9.3. Variables

Table 3. List of Variable Categories

Variable	Role	Data Source	Operational Definition
SSRIs	Exposure	HIRA Database	Prescription claims with a HIRA Drug Main Ingredient code for the following drugs defined in Table 2 will be used individually for each drug: Escitalopram, paroxetine, fluoxetine, sertraline
SNRIs	Exposure	HIRA Database	Prescription claims with a HIRA Drug Main Ingredient code for the following drugs defined in Table 2 will be used individually for each drug: Duloxetine, venlafaxine, desvenlafaxine
Other ADs	Exposure	HIRA Database	Prescription claims with a HIRA Drug Main Ingredient code for the following drugs defined in Table 2 will be used individually for each drug: Mirtazapine, tianeptine, vortioxetine, bupropion
Proportion of Antidepressants	Primary outcome	HIRA Database	For each of 11 study drugs, the following proportions will be calculated 1) Proportion out of total prescriptions in the first 90 days from the index date (acute treatment phase) 2) Proportion out of each gender in the first 90 days from the index date (acute treatment phase) 3) Proportion out of three age groups (≤ 20 , 21-64, ≥ 65) in the first 90 days from the index date (acute treatment phase)

PFIZER CONFIDENTIAL

			
treatment phase)
 
4) Proportion out of 6 subgroups generated by 2 genders and 3 age groups in the first 90 days from the index date (acute treatment phase)

Dosage	Primary outcome	HIRA Database	
For each of 11 study drugs, the following dosages will be calculated
 
 1) Initial dosage at the index date 2) The average dosage during the first 90 day period from the index date (acute treatment phase)
Persistence	Primary outcome	HIRA Database	
For each of 11 study drugs, the average length of treatment on the index drug (allowing 14 day permissible gap) will be calculated
 
 - Switching, combination, augmentation, discontinuation will terminate the persistent period
Discontinuation	Primary outcome	HIRA Database	
For each of 11 study drugs chosen as index drug, the percentage of discontinuation in the first 90 days from the index date (acute treatment phase) will be measured (allowing 14 day permissible gap)

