Adherence	Primary outcome	HIRA Database	
For each of 11 study drugs chosen as index drug, adherence will be measured by MPR during the first 90 days from the index date (acute treatment phase)
 
* MPR = (Days of medication possession from the prescriptions filled in the 90 days) / (90 days + extra days of drug supply from the last prescription fill during the 90 days)
 
** For those period with any identified adverse outcome such as GI bleeding will be considered as

			non-adherent period
Drug utilization pattern in acute phase	Secondary outcome	HIRA Database	
During the first 90 day period starting from the index date, the following types of drug utilization pattern is recorded
 
 - monotherapy (kept on the index medication) - switching (switched to other antidepressant) - combination (adding other antidepressant) - augmentation (adding other non-AD drug such as antipsychotic)
Drug utilization pattern in maintenance phase	Secondary outcome	HIRA Database	
During the second 90 day period (91 ~ 180 days) starting from the index date, the following types of drug utilization pattern is recorded
 
 - choice of antidepressant - monotherapy (kept on the same medication) - switching (switched to other antidepressant) - combination (adding other antidepressant) - augmentation (adding other non-AD drug such as antipsychotic)
Recurrence	Primary outcome	HIRA Database	
Recurrence was operationally defined as either one of the following was satisfied:
 
 1) inpatient episode with a diagnosis code in Table 1 2) emergency room visit with a diagnosis code in Table 1 3) suicide attempt identified by the following KCD-7 codes: 
T40 Poisoning by narcotics and psychodysleptics [hallucinogens] T41 Poisoning by anaesthetics and

PFIZER CONFIDENTIAL

			
therapeutic gases
 
T42 Poisoning by antiepileptic, sedative-hypnotic and antiparkinsonism drugs
 
T43 Poisoning by psychotropic drugs, not elsewhere classified
 
T54 Toxic effect of corrosive substances
 
T60 Toxic effect of pesticides
 
X60-X84 intentional self harm

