1 AMENDMENTS FROM PREVIOUS VERSION(S)

- The status of the study when the amendment is made: During data analysis
- Details and rationale of the changes to the SAP:

Change	Before	After	Rationale
The period of data acquisition	01 Jan 2016 ~ 31 Dec 2019	01 Jan 2017 ~ 31 Dec 2020	To acquire and analyze the latest data available due to the delay of the data acquisition
Inclusion criteria	Patients aged \geq 18 years on the index date	Patients aged \geq 18 years and \leq 70 years on the index date.	Due to a considerable incidence of depression resulting from concomitant diseases in the elderly and limitation of data capacity
MPR	Calculated by (Days of medication possession from the prescriptions filled in the 90 days) / (90 days + extra days of drug supply from the last prescription fill during the 90 days)	Calculated by (Days of medication possession from the prescriptions filled in the 180 days) / (180 days + extra days of drug supply from the last prescription fill during the 180 days)	To lead to more reasonable results that reflects the real-world situation
Operational definition of 'persistence'	For each of 11 study drugs, the average length of treatment on the index drug (allowing a 14-day permissible gap) will be calculated	For each of 11 study drugs, the average length of treatment on the index drug during the first 180-day period (allowing a 14-day permissible gap) will be calculated	Same as above
Operational definition of 'adherence'	For each of 11 study drugs chosen as index drug, adherence will be measured by MPR during the first 90-day period from the index date (acute treatment phase)	For each of 11 study drugs chosen as index drug, adherence will be measured by MPR and persistence during the first 90-day and 180-day period from the index date, respectively (acute treatment phase) - MPR \geq 0.75 and persistence \geq 90 will be considered as adherence	Same as above

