5.1 EFFICACY/EFFECTIVENESS ENDPOINT(S)

Medication compliance (persistence, discontinuation, adherence) along with recurrence are main primary efficacy endpoints and they are defined as follows:

1. MPR (medication possession ratio)
For each of 11 study drugs, the MPR will be calculated by (Days of medication possession from the prescriptions filled in the 180 days) / (180 days + extra days of drug supply from the last prescription fill during the 180 days)
2. Persistence
For each of 11 study drugs, the average length of treatment on the index drug during the first 180 day period (allowing 14 day permissible gap) will be

PFIZER CONFIDENTIAL

calculated. Switching, combination, augmentation, discontinuation will terminate the persistent period.

3. Discontinuation

For each of 11 study drugs chosen as index drug, the percentage of discontinuation in the first 90 days from the index date (acute treatment phase) will be measured (allowing 14 day permissible gap)

4. Adherence

For each of 11 study drugs chosen as index drug, adherence will be measured by MPR and persistence during the first 90 day and 180 day from the index date, respectively (acute treatment phase). MPR ≥ 0.75 and persistence ≥ 90 will be considered as adherence.

* For those period with any identified adverse outcome such as GI bleeding will be considered as a non-adherent period.

5. Recurrence

Recurrence during the acute treatment phase was operationally defined as either one of the following being satisfied:

- 1) Inpatient episode with a diagnosis code in Table 1
- 2) Inpatient episodes via the department of psychiatry or emergency medicine
- 3) Inpatient episode via nursing hospital
- 4) Emergency room visit with a diagnosis code in Table 1
- 5) Suicide attempt identified by the following KCD-7 codes:
 - T40 Poisoning by narcotics and psychodysleptics [hallucinogens]
 - T41 Poisoning by anaesthetics and therapeutic gases
 - T42 Poisoning by antiepileptic, sedative-hypnotic and antiparkinsonism drugs
 - T43 Poisoning by psychotropic drugs, not elsewhere classified
 - T54 Toxic effect of corrosive substances
 - T60 Toxic effect of pesticides
 - X60-X84 intentional self harm
- 6) Augmentation of the following non-AD drugs
 - Antipsychotic: amisulpride, aripiprazole, olanzapine, quetiapine, risperidone, perphenazine
 - Anticonvulsant: carbamazepine, valproic acid, lamotrigine
 - Mood stabilizer: lithium
 - Anxiolytic: buspirone
 - Thyroid hormone: levothyroxine, liothyronine

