Recurrence after the acute treatment phase was operationally defined as either one of the following being satisfied:

- 1) ~6) the same as above
- 7) AD prescription after 30 days of drug holiday

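### Adherence/MPR, persistence and recurrence were redefined during data analysis; no run is planned under the protocol's recurrence or persistence definitions, and the MPR window is contradictory

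*SAP*

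**What the plan says.** SAP section 1 records: "The status of the study when the amendment is made: During data analysis". The reason given for moving MPR to 180 days is "To lead to more reasonable results that reflects the real-world situation". The rows for persistence, adherence and recurrence refer back to that reason.

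Protocol 9.3, Table 3 (Amendment 1, 10 February 2021) still carries the definitions that the SAP replaces:

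- Adherence: "adherence will be measured by MPR during the first 90 days from the index date (acute treatment phase"), with no cut-off.
- Persistence: "the average length of treatment on the index drug (allowing 14 day permissible gap) will be calculated", with no upper time limit.
- Recurrence: "Recurrence was operationally defined as either one of the following was satisfied", followed by three criteria: an admission with a Table 1 diagnosis, an emergency visit with a Table 1 diagnosis, or a suicide attempt by listed codes.

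SAP 5.1 and SAP Table 3 carry the new ones:

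- MPR has the denominator "180 days + extra days of drug supply from the last prescription fill during the 180 days".
- Persistence is "the average length of treatment on the index drug during the first 180 day period (allowing 14 day permissible gap) will be" calculated.
- Adherence becomes a yes/no rule needing MPR of at least 0.75 and persistence of at least 90.
- Recurrence gains admission through psychiatry or emergency medicine, nursing-hospital admission, and augmentation with listed drugs. After the acute phase it also gains "AD prescription after 30 days of drug holiday".

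Protocol 9.7 compares adherence, persistence and recurrence across the 11 drugs, in raw and matched data, and treats p<0.05 as significant. SAP 7.1 and 7.2 describe no sensitivity or parallel analysis under the protocol definitions.

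**The concern.** SAP 5.1 names persistence, discontinuation, adherence and recurrence as the main primary effectiveness endpoints. Three of these four were redefined after analysis had begun, and the reason given concerns how reasonable the results are. The data-period and age-limit changes in the same table have reasons of another kind: data delay, disease in the elderly and data capacity.

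A definition settled during analysis can shift a comparison between drugs, whether or not anyone intends it. If only the amended definition is reported, a reader cannot tell whether a drug ranking, or the link between compliance and recurrence, depends on the change. The second matters because that link is itself part of a primary objective (SAP 2.2).

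**Working it through.** The plan states no figure to reproduce, so the check is mainly a comparison of text.

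**1. How many primary outcomes changed.** Protocol Table 3 labels seven outcomes primary: proportion, dosage, persistence, discontinuation, adherence, recurrence and adverse outcomes. Proportion, dosage, 90-day discontinuation and adverse outcomes keep their definitions in substance. The other three are redefined: 7 − 4 = 3.

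**2. Side by side.**

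| Outcome | Protocol 9.3 | SAP 5.1 and Table 3 |
|---|---|---|
| MPR | 90-day window | 180 days in 5.1(1); 90 days by implication in 5.1(4) |
| Adherence | MPR, no cut-off | MPR ≥ 0.75 and persistence ≥ 90 |
| Persistence | no time limit | first 180 days |
| Recurrence, acute phase | 3 routes | 3 + 3 = 6 routes |
| Recurrence, after acute phase | 3 routes | 6 + 1 = 7 routes |

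The two added admission routes state no Table 1 diagnosis requirement, although the original admission and emergency-visit routes do. As written, an emergency admission unrelated to depression could count as recurrence.

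**3. The MPR window.** SAP 5.1(1) and the MPR row of SAP Table 3 use 180 days. SAP 2.2 keeps the protocol's 90 days. SAP 5.1(4), the adherence row of Table 3 and 7.2.1 pair MPR and persistence with 90 and 180 days through the word *respectively*, which puts MPR at 90.

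To show that this matters, assume back-to-back 30-day fills and then a stop, and read the persistence threshold as days. MPR = days supplied / (window + extra days from the last fill).

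| Days supplied | 90-day MPR | 180-day MPR | Persistence ≥ 90 |
|---|---|---|---|
| 60 | 60/90 = 0.67 | 60/180 = 0.33 | no |
| 90 | 90/90 = 1.00 | 90/180 = 0.50 | yes |
| 120 | 1.00 | 120/180 = 0.67 | yes |
| 150 | 1.00 | 150/180 = 0.83 | yes |

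The 0.75 cut needs 0.75 × 90 = 67.5 days in the shorter window and 0.75 × 180 = 135 in the longer. Adding the SAP's own persistence condition, a patient fully supplied until a stop on days 90 to 134 is adherent on the 90-day reading and non-adherent on the 180-day reading. This is a gap between two readings of the SAP. How many patients fall in it cannot be known from the documents.

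**4. Built-in association.** SAP 5.1 says augmentation ends persistence, and it also lists augmentation as a recurrence route. Suppose a listed drug is added at day 60. Persistence ends at 60, below 90, so the patient is non-adherent and recurrent from a single event. Likewise, a restart after 30 days without an antidepressant presupposes a gap longer than the 14 days allowed (30 > 14), so persistence has already ended. Within the first 180 days, both routes tie recurrence to lost persistence by construction. The protocol's three criteria contain neither route.

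**The case against.** The best case for the sponsor has five parts.

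- **The changes are open.** They are logged with before and after text. The objectives are worded as exploratory and SAP section 3 gives no hypotheses. This lowers the stakes, but Protocol 9.7 still compares drugs on these outcomes with a significance threshold.
- **A 180-day window has a reason unrelated to results.** The second primary objective covers compliance in the maintenance phase, which Protocol Table 3 sets at days 91 to 180, while protocol adherence stops at day 90. This stands as a reason to add a 180-day measure. It does not explain the wider recurrence composite.
- **The 180-day limit on persistence may be the better choice.** Index dates run from 1 January 2018 to 30 June 2019 and data end on 31 December 2020, so follow-up ranges from about 36 down to 18 months. An unlimited average with no stated censoring rule depends on entry date. This stands, and is why the protocol set need not be called primary.
- **The protocol measures partly survive.** The 90-day MPR remains in SAP 2.2, and 7.2.1 lists length of index treatment without repeating the limit. This makes the SAP contradictory on MPR. For persistence, 5.1 and Table 3 state the limit, and no separate unlimited version is planned.
- **The protocol's recurrence also overlaps slightly with compliance.** Self-harm is both a recurrence criterion and an adverse outcome, and adverse-outcome periods count as non-adherent. That overlap is in both definitions; the two described above are new.

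A reader might also infer that the SAP has abandoned the protocol's primary outcomes altogether. It has not: four of the seven are kept.

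**Conclusion.** The point holds for adherence/MPR, persistence and recurrence. Their current SAP definitions date from the analysis stage. The protocol's recurrence and unlimited persistence have no planned run, and the MPR window is unresolved. The countable size is 3 of 7 primary outcomes, and recurrence going from 3 routes to 6 and then 7. The effect on any drug comparison cannot be computed from the documents.

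Two stronger readings are tempting and unsupported. One is that the definitions were chosen after seeing results by drug, or to favour the sponsor's product. The SAP does not say which results were known, the stated reason also appeals to the real-world situation, and nothing shows that any drug gains. The other is that patients stopping between days 68 and 134 move from adherent under the protocol to non-adherent under the SAP. The protocol has no 0.75 cut, so it has no adherent class to leave; the days 90 to 134 result above concerns only the SAP's own two readings.

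The built-in association assumes that adding a listed drug counts as augmentation for persistence, and that a drug holiday means no antidepressant supply. It applies to events in the first 180 days.

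**What to change.** In SAP 5.1, Table 3 and 7.2, report the protocol definitions beside the amended ones for every drug comparison and for the recurrence-compliance analysis. The protocol set is 90-day MPR, three-criterion recurrence, and persistence without the 180-day limit, censored at end of data. Apply both sets to the current SAP cohort.

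Label the amended definitions post hoc. In section 1, state which results, and at what level of detail, were known when each definition was changed. Reconcile the 90- and 180-day MPR windows across 2.2, 5.1(1), 5.1(4), Table 3 and 7.2.1. Which set is called primary may be left to the sponsor.

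The cost is one extra run per endpoint, more tables and a short addition to the SAP. The data period in the SAP (January 2017 to December 2020) covers both sets, so the same extract should serve.

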2 INTRODUCTION

Note: in this document, any text taken directly from the non-interventional (NI) study protocol is *italicised*.

While there are many antidepressants from which physicians can select based on efficacy and tolerability profile, evidence on effectiveness and safety outcomes of new antidepressants in real clinical practice among Korean MDD population is limited.

Hence, the aim of this study is to investigate medication utilization pattern and risk of adverse outcomes among commonly used antidepressants by using nationwide claims database, in order to assess overall clinical benefit of antidepressant therapy in real-world practice.

Research question: *What is the real-world data on antidepressant therapy that can be found in the nationwide claims database in Korea?*

Primary objectives:

1. *Explore baseline characteristics and drug utilization patterns of 11 commonly used antidepressant therapy during 90 days of acute treatment phase*
2. *Explore drug utilization patterns such as therapy changes, medication compliance and recurrence relationship, and risk of adverse outcomes during maintenance phase*

PFIZER CONFIDENTIAL

Secondary objectives:

1. *Choice of antidepressants and drug utilization patterns in patients with various comorbidities*
2. *The relationship of non-pharmacologic treatment and discontinuation, medication compliance*
3. *Choice of antidepressants by non-psychiatric specialty*

[figure not shown]
2.1 STUDY DESIGN

Retrospective cohort study design is used on Subjects who newly initiated antidepressant therapies between Jan 01, 2018 to Jun 30, 2019 in the Health Insurance Review and Service (HIRA) database

**Index date is the first prescription date of study drugs, including SSRIs, SNRIs, and other ADs during the intake period (Jan 01, 2018 to Jun 30, 2019)*

Using a retrospective cohort design, this study will evaluate treatment utilization pattern, medication compliance, incidence of recurrence, risk of adverse outcomes of antidepressant therapy, choice of therapy in various comorbidities, and choice of therapy in other specialty that are recorded in national health insurance database.

Figure 1. Study Design scheme

**Study population**

Subjects who newly initiated antidepressant therapies between Jan 01, 2018 to Jun 30, 2019 in the Health Insurance Review and Service (HIRA) database

PFIZER CONFIDENTIAL

* Index date is the first prescription date of study drugs, including SSRIs, SNRIs, and other ADs during the intake period (Jan 01, 2018 to Jun 30, 2019).

Data source

The Korean HIRA claims data covers 97% of Korean population (about 50 million people) in the Korean National Health Insurance and 3% of Korean population in Medical Aid program.

HIRA claims database from January 01, 2017 to December 31, 2020 will be used for the analysis. It contains the data of universal health insurance system in Korea, wherein patient demographic information, inpatient and outpatient service use, pharmacy dispensing claims, and death can be obtained.

[figure not shown]
The main limitation of HIRA data is lack of clinical lab data and other clinical markers since it is a data collected for claims for reimbursement purpose.

2.2 STUDY OBJECTIVES

Primary objectives:

1. Explore baseline characteristics and drug utilization patterns of 11 commonly used antidepressant therapy during 90 days of acute treatment phase
 - Top 11 commonly used antidepressants according to local market data are as follows:
 - Escitalopram, paroxetine, fluoxetine, mirtazapine, duloxetine, sertraline, venlafaxine, tianeptine, vortioxetine, desvenlafaxine, bupropion
 - Proportion of antidepressants prescribed by sex, age (<20, 21-64, > 65), sex and age combined
 - Initial doses used, average daily doses of each antidepressants
 - Average length of treatment with index medication before therapy change occurs (switching, combination, augmentation, discontinuation)
 - Adherence and persistence measured by medication possession ratio during first 90 days of treatment period
2. Explore drug utilization patterns such as therapy changes, medication compliance and recurrence relationship, and risk of adverse outcomes during maintenance phase
 - The choice of antidepressant, average length of new treatment maintenance, average number of co-administered medications (e.g., atypical antipsychotics, mood stabilizer, thyroid hormone, psychostimulant) when following changes occur from initial monotherapy:
 - Switching
 - Combination
 - Augmentation
 - Medication compliance and recurrence
 - Compliance measured as adherence and persistence
 - Recurrence
 - Relationship between recurrence and compliance

PFIZER CONFIDENTIAL

- *Risk of adverse outcomes measurement between individual ADs that are well known to be treatment-related (e.g., hyponatremia, GI bleeding, fractures, falls, risk of intracranial hemorrhage, attempted suicide/self-harm, myocardial infarction, epilepsy/seizures, stroke/transient ischemic stroke)*

Secondary objectives:

1. *Choice of antidepressants and drug utilization patterns in patients with various comorbidities*
 - *Psychiatric comorbidities*
 - *Mild cognitive impairment (MCI)*
2. *The relationship of non-pharmacologic treatment and discontinuation, medication compliance*
 - *Non-pharmacologic treatments may include: cognitive behavioral therapy (CBT), frequency of physician visit during acute and maintenance phase of treatment*
 - *Frequency of visit during the first 3 months of acute phase and its relationship to treatment maintenance at 4, 5, 6, 7, 8, 9 month time points and discontinuation rate*
3. *Choice of antidepressants by non-psychiatric specialty*
 - *Rheumatology, cardiology, pulmonology, infectious diseases, nephrology, endocrinology and metabolism, gastroenterology, rehabilitative medicine, neurology, neurosurgery, urology, otorhinolaryngology, gynecology & obstetrics, etc.*

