Persistence	Primary outcome	HIRA Database	
For each of 11 study drugs, the average length of treatment on the index drug during the first 180 day period (allowing 14 day permissible gap) will be calculated
 
Switching, combination, augmentation, discontinuation will terminate the persistent period

Discontinuation	Primary outcome	HIRA Database	For each of 11 study drugs chosen as index drug, the percentage of discontinuation in the first 90 days from the index date (acute treatment phase) will be measured (allowing 14 day permissible gap)
Adherence	Primary outcome	HIRA Database	
For each of 11 study drugs chosen as index drug, adherence will be measured by MPR and persistence during the first 90 day and 180 day period from the index date, respectively (acute treatment phase). MPR ≥ 0.75 and persistence ≥ 90 will be considered as adherence.
 
* For those period with any identified adverse outcome such as GI bleeding will be considered as non-adherent period

Drug utilization pattern in acute phase	Secondary outcome	HIRA Database	
During the first 90 day period starting from the index date, the following types of drug utilization pattern is recorded
 
- monotherapy (kept on the index medication)- switching (switched to other antidepressant)- combination (adding other antidepressant)- augmentation (adding other non-AD drug such as antipsychotic)
Drug utilization pattern in maintenance phase	Secondary outcome	HIRA Database	
During the second 90 day period (91 ~ 180 days) starting from the index date, the following types of drug utilization pattern is recorded
 
- choice of antidepressant- monotherapy (kept on the same medication)- switching (switched to other antidepressant)- combination (adding other antidepressant)- augmentation (adding other non-AD drug such as antipsychotic)

PFIZER CONFIDENTIAL

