7.2.4 Relationship between Non-pharmacological Treatments and Antidepressant Compliance Analysis

- To understand the relationship between non-pharmacological treatments and antidepressant compliance among Korean patients with depression
- Secondary analysis
- Endpoints:
 - Medication compliance (adherence, discontinuation, and persistence) by the number of non-pharmacological treatments
- Population: patients who satisfy the acute treatment phase population
- Significance on continuous variables will be tested by ANOVA (if equal variance condition satisfied) or the Kruskal-Wallis H test (otherwise).
- Covariates: antidepressant class covariates such as SSRIs, SNRIs, and other ADs will be used as grouping variables.
- Missing values will be dropped from the analysis.
- The role of this analysis is to provide information on the relationship between non-pharmacological treatments and antidepressant compliance among Korean patients with depression.

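### The compliance measures in SAP 7.2.4 end at day 180 or day 90, so secondary objective 2 gets no result for treatment maintenance at months 7 to 9, although the claims data reach that far

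*SAP*

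**What the plan says.** The objective is current in both documents. Protocol section 8 and SAP 2.2 ask how visit frequency in the first 3 months relates to "treatment maintenance at 4, 5, 6, 7, 8, 9 month time points and discontinuation rate". The SAP's table of amendments does not withdraw it.

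The compliance measures are defined in SAP 5.1 and repeated in Table 3 (SAP 5.4):

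- Persistence is "the average length of treatment on the index drug during the first 180 day period", with a 14-day permissible gap. Switching, combination, augmentation or discontinuation ends it.
- The MPR numerator is "Days of medication possession from the prescriptions filled in the 180 days".
- Adherence is built from MPR and persistence.
- Discontinuation: "the percentage of discontinuation in the first 90 days from the index date (acute treatment phase) will be measured".
- The maintenance-phase utilization pattern is recorded "During the second 90 day period (91 ~ 180 days) starting from the index date".

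SAP 7.2.4 covers the relationship between non-pharmacological treatment and compliance. Its only endpoint line is "Medication compliance (adherence, discontinuation, and persistence) by the number of non-pharmacological treatments".

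On data, SAP 2.1 sets intake from 1 January 2018 to 30 June 2019 and states: "HIRA claims database from January 01, 2017 to December 31, 2020 will be used for the analysis".

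**The concern.** The objective asks for treatment status at six fixed times, the last at nine months. The measures assigned to it stop at six months or earlier. With persistence capped at 180 days, a patient who stops on day 200 and one treated for 300 days have the same value, so their different status at months 7 to 9 is lost.

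The protocol's persistence measure had no upper limit. It was the one compliance measure from which later status might have been derived. The SAP amendment capped it, on the ground that results would be more reasonable and closer to practice, and did not mention this objective.

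If the SAP is followed as written, half of the stated time points go unreported with no statement that they were dropped. The link to visit frequency depends on how a reader interprets 7.2.4.

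**Working it through.** The plan gives no figure of its own on this point, so the check is calendar arithmetic.

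**Step 1. Convert the time points to days and compare them with the windows.** The plan does not define a month, so two conventions are shown. The calendar-month ranges run over all 365 + 181 = 546 possible index dates from 1 January 2018 to 30 June 2019.

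| Month | 30-day months | Calendar months | Within 180 days? | Within 90 days? |
|---|---|---|---|---|
| 4 | 120 | 120–123 | yes | no |
| 5 | 150 | 150–153 | yes | no |
| 6 | 180 | 181–184 | on the limit, or just outside | no |
| 7 | 210 | 212–215 | no | no |
| 8 | 240 | 242–245 | no | no |
| 9 | 270 | 273–276 | no | no |

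Months 7 to 9 lie 210 − 180 = 30 to 276 − 180 = 96 days beyond the persistence and MPR windows under either convention. Three of six points are outside and month 6 is borderline. The 90-day discontinuation measure covers none of the six.

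**Step 2. Effect of the cap.** The recorded value is min(true duration, 180).

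| True duration (days) | Recorded | Truly on treatment at day 210 / 240 / 270 |
|---|---|---|
| 150 | 150 | no / no / no |
| 200 | 180 | no / no / no |
| 240 | 180 | yes / yes / no |
| 300 | 180 | yes / yes / yes |

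The last three patients have different histories and one recorded value.

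**Step 3. Do the data reach month 9?** From the last index date, 30 June 2019, to 31 December 2020 is 366 + 184 = 550 days. The need at month 9 with the 14-day gap is 270 + 14 = 284 days (30-day months) to 276 + 14 = 290 days (calendar months). A patient indexed on 30 June 2019 reaches day 290 on 15 April 2020. All 546 index dates have enough calendar coverage.

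**Step 4. What changed between the documents.**

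| Measure | Protocol | SAP |
|---|---|---|
| Persistence | no upper limit | first 180 days |
| MPR | 90 days | 180 days |
| Discontinuation | 90 days | 90 days |
| Maintenance-phase pattern | days 91–180 | days 91–180 |
| Status at months 4 to 9 | no endpoint defined | no endpoint defined |

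Only persistence was shortened.

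**Step 5. Exposure.** Section 7.2.4 groups patients by number of non-pharmacological treatments. Table 3 defines those by procedure codes and lists number of visits as a separate covariate, which 7.2.4 does not mention. SAP 2.2, however, says that non-pharmacologic treatments may include the frequency of physician visits.

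**The case against.** Three stronger readings are tempting, and the documents do not support them.

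- *A reader might infer that nothing in the SAP looks past day 180.* Two items have no stated end day: the length of the new treatment after a therapy change (SAP 7.2.2), and recurrence through an antidepressant restart after a 30-day break (SAP 5.1). Section 7.2.2 also lists compliance in the maintenance phase. None of these gives status at fixed months by visit frequency, so the gap remains, but the universal claim is wrong.
- *A reader might infer that there will be no visit-frequency result at all.* SAP 2.2 allows visits to count as non-pharmacologic treatment, and Table 3 has a visits covariate. The fair statement is that 7.2.4 does not explicitly name visit frequency.
- *A reader might infer that the amendment alone lost the objective.* The 90-day discontinuation window comes from the protocol, and the protocol never defined a monthly status endpoint. The SAP lengthened MPR. Under the protocol's dates (intake to 30 June 2019, data to 31 December 2019) the last patients had only 184 days; 805 of 911 index dates (88.4%) reached day 290. Full coverage is a feature of the SAP's later data period.

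It can also be said that this is one sub-item of a secondary, exploratory objective with no hypotheses, and that text between SAP 5.2 and 5.4 is blacked out and could hold a further endpoint. Both stand. The first limits the importance. The second limits certainty, though neither Table 3 nor 7.2.4 refers to such an endpoint.

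**Conclusion.** The point holds. The compliance measures that 7.2.4 uses give no treatment status at months 7, 8 and 9, three of the six time points in the objective, and month 6 is at the limit. Section 7.2.4 names neither the monthly time points nor, explicitly, the visit-frequency exposure. This is more than missing detail, because a stated 180-day rule conflicts with a stated objective that the available claims could answer.

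The conclusion assumes that the blacked-out text holds no relevant endpoint. The 550 days are calendar coverage; death or loss of insurance could shorten follow-up for individuals. No primary result is affected. The SAP should be changed, but the study's main findings do not depend on it.

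**What to change.** Keep 180-day persistence as defined, and add one endpoint to SAP 5.1, Table 3 and 7.2.4:

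- **Endpoint:** on treatment (yes/no) at days 120, 150, 180, 210, 240 and 270, with the 14-day gap, following claims to at least day 284. If calendar months are preferred, say so and follow to day 290.
- **Meaning of on treatment:** state whether it is the index drug or any antidepressant. This matters because switching, combination and augmentation end persistence under the current rule.
- **Exposure:** number of visits in days 1 to 90, among patients still on treatment at day 90. Without that restriction, patients who stop early would tend to have fewer visits because they stopped, and the association would be partly built in.
- **Label:** the SAP was amended during data analysis, so record the endpoint as added at that stage.

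The cost is SAP wording and one derived variable from data within the study period, with no new patients or data years. The small downside is the late-addition label. If the sponsor does not add the endpoint, months 7 to 9 should be formally dropped from the objective.
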